Grade I Hematological Toxicity	Maintain original dose		
Grade II Hematological Toxicity	Maintain original dose		
Grade III Hematological Toxicity	Interrupt treatment and give symptomatic treatment until toxicity returns to Grade \leq II, and then resume treatment at the original dose level	After treatment discontinuation during treatment cycle, hematological toxicity must recover to Grade \leq II before treatment can be resumed	At the beginning of the next cycle of administration, hematological toxicity must recover to Grade \leq II before treatment can be started
Grade IV Hematological Toxicity	Interrupt treatment and give symptomatic treatment until toxicity returns to Grade \leq II, and then resume treatment at the next lower dose level; upon complete recovery of toxicity, dose may be re-adjusted to the previous level to continue treatment; if a Grade IV hematological toxicity occurs again after such re-adjustment, dose should be reduced accordingly and no further adjustments shall be allowed		
Grade I Non-Hematological Toxicity	Maintain original dose		
Grade II Non-Hematological Toxicity	Give symptomatic treatment and continue study administration at the same time, if toxicity returns to Grade \leq I after one week, continue dosing; if the toxicity does not recover or even worsens, interrupt treatment until toxicity returns to Grade \leq I, and then resume treatment at the original dose level	After treatment discontinuation during treatment cycle, non-hematological toxicity must recover to Grade \leq I before treatment can be resumed	At the beginning of next cycle, non-hematological toxicity must recover to Grade \leq I before treatment can be started
Grade III Non-Hematological Toxicity	Interrupt treatment and give symptomatic treatment until toxicity returns to Grade \leq I, and then resume treatment at the original dose level, and reduce by 1 dose level for the next cycle; investigator may decide accordingly for certain patients based on the specific conditions without waiting for the next cycle; upon complete recovery of toxicity, dose may be re-adjusted to the previous level to continue treatment; if a Grade III non-hematological toxicity occurs again after such re-adjustment, dose should be reduced accordingly and no further adjustments shall be allowed		

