NCI Toxicity Grade	Regulations for Dose Modification	Regulations for Toxicity Recovery upon Re-Administration after Treatment Discontinuation	Regulations for Toxicity Recovery at the Beginning of Next Cycle
Grade IV Non-Hematological Toxicity	Interrupt treatment and give symptomatic treatment until toxicity returns to Grade \leq I, and then resume treatment at the next lower dose level for at least 1 cycle; upon complete recovery of toxicity, dose may be re-adjusted to the previous level to continue treatment; if a Grade IV non-hematological toxicity occurs again after such re-adjustment, dose should be reduced accordingly and no further adjustments shall be allowed (if a life-threatening adverse reaction, such as Grade IV renal impairment, neurotoxicity, cardiotoxicity, or hepatotoxicity occurs, discontinue the treatment and withdraw)		

ABBREVIATIONS AND DEFINITIONS

The following abbreviations and special terms are used in this study protocol

Abbreviations and Special Terms	Definitions
ACEI	Angiotensin converting enzyme inhibitor
AE	Adverse event
AFP	Alpha-Fetoprotein
AKP	Alkaline phosphatase
ALT	Alanine aminotransferase
ANC	Absolute neutrophil count
APTT	Activated partial thromboplastin time
ARB	Angiotensin II receptor blocker
AST	Aspartate aminotransferase
BUN	Blood urea nitrogen
B-Scan	B-mode ultrasound
Ca	Calcium
Cl	Chlorine
Cr	Creatinine
CR	Complete response
CT	Computed tomography
DCR	Disease control rate
DLT	Dose-limiting toxicity
DRQ	Data ready queue
ECOG PS	Eastern Cooperative Oncology Group Performance Status
eCRF	Electronic case report form
EGFR	Epidermal growth factor receptor
Fbg	Fibrinogen
GCP	Good Clinical Practice
FAS	Full analysis set
Glu	Glucose
Hb	Hemoglobin
HCC	Hepatocellular carcinoma
HFS	Hand-foot-skin reaction
HMG-CoA	β -Hydroxy β -methylglutaryl-coenzyme A
ITT	Intention to treat
K	Potassium
LD50	Median lethal dose
MRI	Magnetic resonance imaging
MTD	Maximum tolerated dose
Na	Sodium
NCI-CTC	National Cancer Institute Common Toxicity Criteria
OB	Occult blood
ORR	Objective response rate
OS	Overall survival
PD	Progressive disease
PDGFR	Platelet derived growth factor receptor
PFS	Progression free survival

Abbreviations and Special Terms	Definitions
PI	Principal investigator
PLT	Platelet
PR	Partial response
PRO	Protein
PPS	Per-protocol set
PT	Prothrombin time
q.d.	Quaque die
QoL	Quality of life
RBC	Red blood cell
RC	Red color sign
RECIST	Response evaluation criteria in solid tumors
RR	Response rate
RTKs	Receptor tyrosine kinase

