7 CRITERIA FOR DOSE INTERRUPTION AND MODIFICATION

7.1 Dose Level and Use of Drugs

The dose levels in the treatment and placebo groups are: 1) starting dose: 750 mg, q.d.; 2) second dose level: 500 mg, q.d.; 3) third dose level: 250 mg, q.d. The initial dose of each group can be reduced by two levels. After dose reduction, the dose can be resumed to the previous dose level if the toxicity is completely recovered; if the dose is reduced again, no further modification is allowed. The administered doses and dose modification of each group are shown in the table below, and the dose can be modified according to the "Dose Modification" column shown below.

Table 8. Doses and dose level modification of each group

	Treatment Group	Placebo Group
Starting dose	■■■	□□□
First dose reduction	■■	□□
Dose re-modification Toxicity recovery ^a	■■■	□□□
Second dose reduction ^b	■■	□□
Third dose reduction	■	□
Dose re-modification Toxicity recovery ^a	■■	□□
Fourth dose reduction ^b	■	□

Note: ■ = Apatinib mesylate tablets 250 mg/tablet, □ = Apatinib mesylate dummy tablets

a After dose reduction, the dose can be resumed to the previous dose level if the toxicity is completely recovered;

b If the dose is reduced again, it should not be resumed again.

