7.2 Dose Modification

According to the results of the phase I clinical trial of apatinib, considering that the exposure levels in men and women are different after apatinib administration, and that the drug shows certain individual differences, the dose of apatinib should be modified appropriately in the trial (assuming continuous administration). The treatment can be interrupted in terms of drug toxicity and be resumed after the toxicity is alleviated; the dose can also be reduced and be resumed to the previous dose level after the toxicity has been completely recovered; if the dose is reduced again due to toxicity, it should not be resumed again. The final study report should include statistics of the dose intensity and time of treatment interruption. Specific rules are as follows:

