7.2.6 Discontinuation criteria based on liver function

1) If the subject has $ALT > 5 \times ULN$ and total bilirubin $> 2 \times ULN$, the following measures must be taken:

(1) Immediately discontinue the use of the investigational drug and give active symptomatic treatments;

(2) Complete the SAE form and handle it in accordance with the requirements for SAE in Section 11 of this protocol;

(3) Follow-up the event according to the requirements for "Follow-up of Adverse Events" in Section 4 of this protocol, and check liver function every week until it returns to the baseline level;

7.3 If the subject experiences any of the following conditions:

$ALT > 8 \times ULN$ or $ALT > 5 \times ULN$ for more than 2 weeks: The patient must be reexamined within 3 days after the first occurrence of the event, and then reexamined weekly to monitor whether the ALT value continues to increase. If the ALT value continues to increase, the use of the apatinib should be interrupted. The liver function should be reexamined within 2 weeks. If the treatment is effective and the subject is willing to continue to receive the apatinib treatment after obtaining the results of the liver function test, the subject can resume the apatinib treatment at the next lower dose level after obtaining the permission of the investigator and the medical director of the sponsor, and the liver function of the patient should be monitored every 2 weeks until it returns to the baseline level.

Other rules

To ensure the consistency of dose modifications throughout the study, treatment should be first discontinued before undergoing a dose modification for each dose cycle. The dose can only be reduced if the subject still cannot tolerate the dose after dose interruption.

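### The study-wide Other rules sentence on dose reduction, on its most natural literal reading, conflicts with the dose modification table after Grade IV and Grade III non-hematological toxicity, and no text says which governs

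*Protocol*

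**What the plan says.** The Regulations for Dose Modification table, placed after the Schedule of Activities in the Protocol, sets the action by toxicity grade. For Grade IV hematological toxicity it orders interruption until recovery to Grade II or lower, "and then resume treatment at the next lower dose level; upon complete recovery of toxicity", the dose may go back up. For Grade IV non-hematological toxicity it orders interruption until recovery to Grade I or lower, "and then resume treatment at the next lower dose level for at least 1 cycle". Life-threatening reactions are excepted: if one "such as Grade IV renal impairment, neurotoxicity, cardiotoxicity, or hepatotoxicity occurs, discontinue the treatment and withdraw". For Grade III non-hematological toxicity it orders interruption until recovery to Grade I or lower, "and then resume treatment at the original dose level, and reduce by 1 dose level for the next cycle", and the investigator may act without waiting for that cycle.

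The Other rules paragraph follows the liver-function rules (Section 7.2.6 and the ALT text numbered 7.3). Its first sentence gives its scope: "To ensure the consistency of dose modifications throughout the study, treatment should be first discontinued before undergoing a dose modification". Its second reads: "The dose can only be reduced if the subject still cannot tolerate the dose after dose interruption".

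Two general passages bear on the relation between them. Section 7.1 says of the dose levels, "and the dose can be modified according to the" Dose Modification column. Section 7.2 says that, for toxicity, "the dose can also be reduced and be resumed to the previous dose level after the toxicity has been completely recovered".

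**The concern.** The table's reductions after Grade IV toxicity, and in the cycle after Grade III non-hematological toxicity, carry no condition that the patient fail the dose again. The Other rules sentence appears to add exactly that condition, for the whole study. A site reading it literally could return a patient who has recovered from a Grade IV event to the dose that caused it. A site following the table would depart from a rule stated as study-wide.

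The restart dose after Grade IV toxicity is a safety instruction, so a site should not have to choose between two texts. If sites choose differently, dose intensity (SAP Appendix 3), the grading of study-drug deviations (SAP Appendix 1) and recurrent severe toxicity could partly reflect which text a site followed.

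**Working it through.** The documents give no figure to reproduce. The check sets the two texts side by side and then looks for a rule that ranks them.

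**Step 1: each row of the table against the Other rules sentence, read literally.**

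| Toxicity | Table | Conflict? |
|---|---|---|
| Grade I; Grade II hematological | Dose unchanged | No |
| Grade II non-hematological | One week of symptomatic treatment while dosing; if not recovered, interrupt and restart at the same dose | No |
| Grade III hematological | Interrupt, restart at the same dose | No |
| Grade III non-hematological | Interrupt, resume the same dose, lower one level in the next cycle | Yes, if the resumed dose is tolerated |
| Grade IV hematological | Interrupt, restart one level lower | Yes |
| Grade IV non-hematological, no withdrawal | Interrupt, restart one level lower for at least one cycle | Yes |
| Grade IV, life-threatening reaction | Withdraw | No |

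In the Grade IV rows the patient has recovered and has not retried the dose, so a condition of still not tolerating it after the interruption is not met. In the Grade III non-hematological row the dose has been retried. If it is tolerated, the sentence withholds the reduction that the table orders. If toxicity recurs, both texts allow a reduction.

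**Step 2: can another reading remove the conflict?**

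- *Interrupt before reducing.* This fits the table, because every Grade III and IV row begins with interruption. But the preceding sentence already says it, so the second sentence would add nothing and its limiting words would have no effect.
- *Toxicity persists despite the interruption.* This does not fit, because the table requires recovery before any restart.

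The protocol does spell out a same-dose retrial where it wants one. Section 7.2.5 resumes at the same dose after QTcF recovery and reduces only if prolongation returns. The Grade III hematological and Grade II non-hematological rows also restart at the same dose. The Grade IV rows are written differently.

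**Step 3: does any text rank the two?** Section 7.1 is a permissive pointer to a column. Section 7.2 is a general introduction that announces specific rules to follow. Section 7.2.1 sets the grades from which interruption and reduction are allowed, and Section 7.2.3 limits the number of reductions. None ranks the table against Other rules, and the SAP is silent.

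**Step 4: the dose in dispute** (dose levels from Section 7.1).

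- Starting level: 750 / 500 = 1.5 times the table's dose.
- Second level: 500 / 250 = 2.0 times the table's dose.

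For Grade IV toxicity this is the restart dose. For Grade III non-hematological toxicity it is the next-cycle dose.

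**The case against.** The best counter-argument is that the sentence need not be a prohibition. The protocol's only definition of intolerance (Section 3.2, inclusion criterion 3) includes Grade IV or higher hematological and Grade III or higher non-hematological toxicity, which are the rows where the table steps down. On that vocabulary such a patient is already intolerant of the dose. The sentence before it is about sequence, Section 7.1 points to the table, and the text is a translation, so weight on single words is risky. Section 7.2 adds little to the conflict, since an introduction may leave out a condition supplied later.

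Much of this stands, and it lowers confidence from high to moderate. It does not dispose of the point. The intolerance definition is written for prior therapy, and the sentence asks about tolerance after the interruption, not at the event. A pointer that says the dose can be modified by the table does not say that the table prevails.

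It is also fair that the harm is not demonstrated. The sentence does not itself order a restart at 750 mg, life-threatening Grade IV reactions lead to withdrawal, and the investigator has discretion over timing in the Grade III row. Dosing is double-blind with the same rules in both arms, so differing site practice is not shown to bias the comparison.

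**Conclusion.** The two texts do not fit together on the most natural literal reading of the sentence, and nothing says which governs. This is a safety and conduct inconsistency that should be fixed, held with moderate confidence. The dose at stake is 1.5 or 2 times the dose that the table orders. This rests on reading the sentence as a condition on reduction and not only as a statement of sequence.

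Three stronger conclusions are tempting, and the documents do not support them:

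- *The protocol clearly forbids these reductions.* It does not, because a softer reading is available and Section 7.1 points the other way.
- *The phase II data show how many patients are affected.* Table 5 of the Protocol gives Grade III–V drug reactions in 30/51 = 58.8% at 750 mg, but it splits neither by grade nor into hematological and non-hematological events. It mixes disputed cases with undisputed ones, so the number affected is unknown.
- *The primary result is at risk.* Overall survival is analyzed in the FAS by randomized group with a stratified log-rank test (SAP Sections 6.1 and 7.3.1), and that analysis does not depend on which dose rule a site followed.

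The step-downs for LVEF (Section 7.2.4) and ALT (7.3) are also hard to square with the sentence, but they are permissive. The proteinuria advice in Table 11 is for reference only. The conclusion does not rest on any of these.

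**What to change.** Replace the second sentence of Other rules with:

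> Withdrawal and discontinuation rules apply first. Dose reductions follow the dose modification table, or Sections 7.2.4–7.3 where these specify a restart dose; reductions ordered there do not require failure of the same dose again. Where the table orders interruption and restart at the original dose (Grade III hematological toxicity, or Grade II non-hematological toxicity not recovered after one week of symptomatic treatment), the dose may be reduced one level only if the toxicity recurs or is not tolerated after restart. Grade I toxicity and Grade II hematological toxicity: maintain the original dose, as in the table.

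This gives the retrial condition a place where it does no harm: the two rows in which Section 7.2.1 allows a reduction but the table orders none. The named exceptions matter. Without them, a literal reader could interrupt treatment for Grade I or Grade II hematological toxicity, which Section 7.2.1 does not allow, or skip the week of symptomatic treatment for Grade II non-hematological toxicity. Table 11 stays advisory.

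The cost is one replacement paragraph in the protocol and a memo to sites, with no new data, visits or patients.

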8 CONCOMITANT MEDICATION

8.1 Medications Prohibited or Used with Caution during the Study

8.1.1 Drugs that interfere with liver P450 enzymes

Apatinib has a strong inhibitory effect on CYP3A4, YP2C9 and CYP2C19 ($IC_{50} < 0.5 \mu M$). Omeprazole should be used with caution during the treatment. CYP3A4 inducers (carbamazepine, rifampicin and phenobarbital) and inhibitors (ketoconazole, itraconazole, erythromycin and clarithromycin), CYP3A4 substrates (simvastatin, cyclosporine and pimozide), and other drugs metabolized via CYP3A4 (such as benzodiazepines, dihydropyridine, calcium ion antagonist and HMG-COA reductase inhibitors) should be used with caution. CYP2C9 substrates (diclofenac, phenytoin, piroxicam, S-warfarin, and tolbutamide) and CYP2C19 substrates (diazepam, imipramine, lansoprazole, and S-mephenytoin) should be used with caution.

8.1.2 Drugs that prolong the QT interval of the heart

As tinib drugs may cause toxicities of prolonged QT interval in clinical applications, drugs that may prolong the QT interval should be used with caution during the trial, including antibiotics, antiarrhythmics, antipsychotics, antifungal drugs, antimalarial drugs, and antidepressants (such as clarithromycin, quinidine, risperidone, fluconazole, mefloquine, amitriptyline, azithromycin, sotalol, fluphenazine, ketoconazole, chloroquine, imipramine, erythromycin, amiodarone, droperidol, clomipramine, roxithromycin, disopyramide, haloperidol, dosulepin, metronidazole, procainamide, thioridazine, doxepin, moxifloxacin, pimozide, olanzapine, and clozapine).

8.1.3 Traditional Chinese medicine and immunological agents with anticancer effects

NMPA-approved Chinese medicine preparations for liver cancer (including Delisheng injection, Kanglaite injection, Aidi injection, Huaier granule, GFL tablets) and immunomodulators (interferon and interleukin-2) are prohibited during the trial.

8.2 Medications and Treatments that May be Used Concomitantly during the Trial

The patient could receive the best supportive care. Bisphosphonates for bone metastasis is permitted while the subject is receiving study medication. If systemic or local analgesia is not effective in controlling painful lesions of bone metastases, a small area of palliative radiotherapy (the area of the radiotherapy must be $<5\%$ of the bone marrow region, and the percent bone marrow in human skeleton is shown in the figure of Appendix 8) is allowed. Comorbidities and various AEs should be actively treated. All concomitant medications should be documented in the eCRF in strict accordance with the GCP regulations.

8.3 Recommended Symptomatic Treatment for Common Adverse Drug Reactions

8.3.1 Hand-foot-skin reaction

Hand-foot-skin reaction (HFSR) is a skin toxicity with palmar-plantar dysesthesia or acral erythema and manifests especially in areas under pressure or force. It may occur in patients with tumor during chemotherapy or molecular targeted therapy. HFSR is characterized by numbness, dysesthesia, paraesthesia, tingling, no pain or pain, skin swelling, or erythema, desquamation, chapping, scleroma-like blisters, and severe pain.

Grading of HFSR:

Grade 1: numbness/dysesthesia/paraesthesia, painless swelling or erythema of the hands and/or feet and/or discomforts that does not affect normal activities.

Grade 2: painful erythema and swelling of the hands and/or feet and/or discomforts affecting patients' activities of daily living.

Grade 3: wet desquamation, ulcers, blisters or severe pain of hands and/or feet and/or severe discomfort that causes the patients to be unable to work or perform activities of daily living. Intense pain and loss of skin function, relatively rare.

Symptomatic treatment and management of HFSR:

Some necessary symptomatic and supportive treatments must be taken, including: strengthen skin care, keep skin clean, and avoid secondary infections; avoid pressure or friction; use moisturizers or lubricants, topically use lotions or lubricants containing urea and corticosteroids; topically use antifungal or antibiotic treatment if necessary.

8.3.2 Hypertension

Management of treatment-related hypertension

- Monitoring and handling of hypertension: Blood pressure should be monitored once a week during the first 6 cycles of the targeted pharmacological treatment. Once hypertension occurs, the following standard treatments can be given: Angiotensin II receptor blocker (ARB), angiotensin converting enzyme inhibitor (ACEI), beta blocker, diuretics, etc., or the combined application of above drugs.
- Preferably selected medications (drugs not metabolized through the liver):
 - 1) Valsartan (Diovan), 80–320 mg q.d.;
 - 2) Atenolol (Tenormin), 50–100 mg q.d.;
 - 3) HCTZ (Hyzaar), 12.5–100 mg q.d.;
 - 4) Telmisartan (Micardis), 20–80 mg q.d.;
 - 5) For those with difficulty controlling blood pressure: Amlodipine (Norvasc), 2.5–10 mg q.d.

Clinical staging of hypertension and routine treatment at each stage

- Pre-hypertension: (120–139/80–89 mmHg, or a systolic blood pressure of 120–139 mmHg)
There is no indication for the use of antihypertensive drugs, and only blood pressure monitoring is needed;
- Grade 1 hypertension: (140–159/90–99 mmHg, or a systolic blood pressure of 140–159 mmHg)
Use of antihypertensive drugs and monitoring of blood pressure; most patients use thiazide-type diuretics, while ARB, ACEI, β blockers and calcium channel blockers can also be considered;
The administration of apatinib can be continued, and a combination of two antihypertensive drugs can be considered if the antihypertensive effect is not ideal.
- Grade 2 hypertension: (160–179/100–109 mmHg, or a systolic blood pressure of 160–179 mmHg)
Combination use of two drugs (usually a combination of thiazide-type diuretics with ARB, ACEI, β blockers, or calcium channel blockers); monitoring of blood pressure;
- Grade 3 hypertension: (\geq 180/110 mmHg, or a systolic blood pressure of \geq 180 mmHg)
Combination use of two drugs (usually a combination of thiazide-type diuretics with ARB, ACEI, β blockers, or calcium channel blockers); the blood pressure is closely monitored; other risk factors (such as target organ damage, diabetes and other accompanying clinical symptoms) are evaluated, and appropriate measures are taken;
- Hypertensive crisis: Refers to a serious clinical condition featured by an excessively elevated blood pressure and a diastolic blood pressure exceeding 16.0–17.3 kPa (120–130 mmHg). At present, there is no unified classification of hypertensive crisis in China and abroad. Recently, hypertensive crisis is usually divided into two types from the perspective of clinical treatment: (1) Hypertension emergencies: A diastolic blood pressure of $>$ 16.0 kPa (120 mmHg), accompanied with acute or progressive target organ damage, such as cerebral infarction, intracranial or subarachnoid hemorrhage, and hypertensive encephalopathy, etc. Among them, progressive or acute hypertension based on chronic essential hypertension is the most common (about 40%–50% of all cases). (2) Hypertension urgencies: A diastolic blood pressure of $>$ 16.0 kPa (120 mmHg) without or with only slight organ damage; in such patients, sodium nitroprusside or nifedipine is used to rapidly reduce the blood pressure, diazepam and phenobarbital are used to prevent seizures, and furosemide and mannitol are used to induce dehydration and reduce intracranial pressure, etc.;

Note: For those with hypertensive crisis, the application of apatinib should be discontinued immediately and the subjects should withdraw from this clinical trial.

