11. Women of childbearing potential must have a negative pregnancy test (serum or urine) within 7 days prior to enrollment, and be willing to take appropriate contraceptive measures during the trial and within 8 weeks after the last dose of the investigational drug. Male subjects should either undergo surgical sterilization, or agree to take

appropriate contraceptive measures during the trial and within 8 weeks after the last dose of the investigational drug;

12. Subjects must participate voluntarily, sign the informed consent form, have good compliance and corporate with follow-up visits.

3.3 Exclusion Criteria:

1. Patients who have received any local treatment within 4 weeks prior to participating in this study (including but not limited to surgery, radiation, hepatic artery embolization, TACE, hepatic arterial infusion, radiofrequency ablation, cryoablation, or percutaneous ethanol injection);
2. Patients with known intrahepatic cholangiocarcinoma, mixed hepatocellular carcinoma and fibrolamellar hepatocellular carcinoma; other uncured malignancies currently or within the past 5 years, except for cured skin basal cell carcinoma or cervical carcinoma in situ;
3. Patients planning to receive liver transplant (except for patients who have undergone liver transplant);
4. Patients with symptomatic ascites requiring therapeutic paracentesis or drainage, or with a Child-Pugh score > 2;
5. Patients with hypertension which cannot be controlled to the normal range by antihypertensives (systolic pressure > 140 mmHg, diastolic pressure > 90 mmHg);
6. Patients with Grade II or greater myocardial ischemia or myocardial infarction, uncontrolled arrhythmias (QTc interval \geq 450 ms in males and \geq 470 ms in females);
7. Patients with NYHA (see Appendix 5) Class III-IV cardiac insufficiency or LVEF (left ventricular ejection fraction) < 50% by echocardiography;
8. Presence of multiple factors affecting oral medications (such as inability to swallow, chronic diarrhea, and intestinal obstruction, which significantly affect drug administration and absorption);
9. Patients with a history of gastrointestinal bleeding within the past 6 months or a high risk of bleeding such as esophageal varices with bleeding risk, active ulcers, and fecal occult blood \geq (++); in the case of fecal occult blood (+), a gastroscopy is required;
10. Abdominal fistula, gastrointestinal perforation or abdominal abscess within 28 days prior to the study;

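### In the reference-only blood pressure list of Protocol 8.3.2 the printed diastolic ranges have no effect, so readings such as 135/95 fall only in the row that advises no drug

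*Protocol*

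**What the plan says.** Protocol section 8.3.2 gives a staging list with a suggested treatment for each stage. The lowest row is "Pre-hypertension: (120–139/80–89 mmHg, or a systolic blood pressure of 120–139 mmHg", and its advice is "There is no indication for the use of antihypertensive drugs, and only blood pressure monitoring is needed". The next two rows are "Grade 1 hypertension: (140–159/90–99 mmHg, or a systolic blood pressure of 140–159 mmHg", for which antihypertensive drugs are advised, and "Grade 2 hypertension: (160–179/100–109 mmHg, or a systolic blood pressure of 160–179 mmHg", for which two drugs are combined. The Grade 3 row has the same form, with 180/110 mmHg or above as the pair and a systolic value of 180 mmHg or above as the alternative; it also advises two drugs.

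A separate entry for hypertensive crisis follows. It is the only entry in the list that uses diastolic pressure on its own. Its two subtypes both start above 120 mmHg, and its Note directs that apatinib be stopped and the subject withdrawn.

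Elsewhere, exclusion criterion 5 (Protocol section 3.3) describes hypertension that "cannot be controlled to the normal range by antihypertensives (systolic pressure > 140 mmHg, diastolic pressure > 90 mmHg".

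**The concern.** A blood pressure staging list should respond to either component of the reading. In this one, every row offers the systolic range as a sufficient condition by itself, and no row offers the diastolic range as one. A patient whose systolic pressure stays at 120–139 mmHg while the diastolic rises to 90 mmHg or more is then placed in the row that says no drug is indicated. That is advice against treatment, which is different from silence.

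Hypertension is a named event of special interest (Protocol synopsis; SAP section 7.4.1). In the phase II HCC trial at 750 mg, the starting dose here, 25 of 51 patients (49.0%) had hypertension and 7 (13.7%) had it at Grade III–V (Protocol Table 6). Sites can be expected to consult this section. What is at stake is the clarity of patient-safety guidance, not an analysis.

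**Working it through.** No sample size, power or alpha calculation applies. The check is one of logic, with inputs from the four rows of section 8.3.2.

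**Step 1: the form of each row.** Let S mean that the systolic value is in the row's range and D that the diastolic value is. Each row reads (S and D) or S. This equals S, whatever D is.

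**Step 2: enumeration.** Take systolic 80–260 mmHg (181 values), diastolic 40–160 mmHg (121 values) and four rows: 181 × 121 × 4 = 87,604 comparisons of the printed rule with a systolic-only rule. They disagree in 0.

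**Step 3: individual readings.** The last column words each row as systolic range or diastolic range and takes the highest row met.

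| Reading (mmHg) | Row met as printed | Row whose diastolic range contains the value | Row if reworded |
|---|---|---|---|
| 135/85 | Pre-hypertension | Pre-hypertension | Pre-hypertension |
| 135/95 | Pre-hypertension | Grade 1 (90–99) | Grade 1 |
| 138/105 | Pre-hypertension | Grade 2 (100–109) | Grade 2 |
| 138/115 | Pre-hypertension | Grade 3 (110 or above) | Grade 3 |
| 150/105 | Grade 1 | Grade 2 (100–109) | Grade 2 |
| 118/95 | None | Grade 1 (90–99) | Grade 1 |

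So 135/95 sits one row below its printed diastolic range (no drug instead of antihypertensive drugs), and 138/105 sits two rows below (no drug instead of two drugs).

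**Step 4: upper limit.** Above 120 mmHg diastolic the crisis entry applies on diastolic pressure alone. The readings that meet only the no-drug row therefore have systolic 120–139 and diastolic 90–120 mmHg, without being open-ended upwards.

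**Step 5: comparison with exclusion criterion 5.** That criterion names diastolic above 90 mmHg as outside the normal range. The two examples exceed it by 95 − 90 = 5 mmHg and 105 − 90 = 15 mmHg. It governs entry, not treatment on study, so it shows only that the protocol elsewhere counts diastolic pressure in its own right.

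**Step 6: the other reading of the slash.** If 120–139/80–89 meant either component, 135/95 would meet both the pre-hypertension and the Grade 1 rows, and 138/105 both the pre-hypertension and the Grade 2 rows. The advice would conflict, with no rule for which row prevails. This is not usual blood pressure notation, and the list would still need rewording.

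**The case against.** The strongest reply is that nothing binding withholds treatment. The closing Note in section 8.3.5 marks these suggestions as reference only and refers the reader to a specialist. Section 8.2, which that Note does not cover, says that comorbidities and AEs are to be treated actively. AEs are graded by NCI-CTCAE 4.0 (section 11.2). Dose changes follow NCI grade, with symptomatic treatment from Grade II non-hematological toxicity upwards (Regulations for Dose Modification). Abnormal blood pressure is followed daily (section 9.2). All of this stands, and it keeps the point small. It does not make the row correct.

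A second reply is that section 8.3.2 opens by allowing standard antihypertensives once hypertension occurs. That helps only in part: the list labels 135/95 pre-hypertension, so the condition is not clearly met, and the wording is permissive.

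A third is that the text is a translation, and that a clause repeating the systolic range in all four rows looks like a slip for 'diastolic'. That is plausible. The documents cannot confirm it, and the same rewording would restore that meaning.

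A reader might also infer a conflict at, say, 155/122, where the Grade 1 row states "The administration of apatinib can be continued, and a combination of two antihypertensive drugs can be considered" while the urgency subtype covers diastolic pressure above "16.0 kPa (120 mmHg) without or with only slight organ damage" and the Note says "For those with hypertensive crisis, the application of apatinib should be discontinued immediately and the subjects should withdraw from this clinical trial". The documents do not support this as a separate fault. The Grade 1 wording is general and permissive; the Note is specific and directive, and on an ordinary reading it governs.

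**Conclusion.** The point holds as a minor wording fault in advisory text. As printed, the diastolic ranges in the four staged rows do nothing, and systolic 120–139 with diastolic 90–120 mmHg meets only the row advising no antihypertensive, against the list's own higher rows. This rests on reading the slash as the usual systolic/diastolic pair; on the alternative reading the fault becomes contradictory advice.

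The size can be stated only for a reading, one to three rows too low in the examples with systolic 120–139 mmHg. The documents do not separate systolic from diastolic elevations, so no number of patients can be derived, and the phase II incidence is not an estimate of it.

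Two stronger inferences are not supported. One is that the protocol forbids treating such patients: the list does not bind, and section 8.2 points the other way. The other is that AE grades, dose modification, OS, alpha or power are affected: none of them uses this list.

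**What to change.** In section 8.3.2, reword each row as systolic X or diastolic Y mmHg, using the diastolic ranges already printed (80–89, 90–99, 100–109, and 110 or above). Add that the higher row applies when the two values point to different rows. Leave diastolic readings above 120 mmHg under the existing crisis entry. Check the source-language text to see whether the repeated 'systolic' arose in translation.

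The cost is a wording change to one list in the protocol. It needs no new measurement and no change to the SAP.
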